**5 IU of Insulin**

**10 IU of Insulin**

## Assessment

**Potassium** level: 0 and 120 minutes.  
**Blood sugar:** 0, 60 and 120 minutes.  
Report any adverse event

## Termination

The study will be over at 120 min from medication administration

## Hypoglycemia management flow chart

**Hypoglycemia, RBS  $\leq$  3.89 mmol/l in DM patient or RBS  $\leq$  3 mmol/l in nonDM patient**

**Alert**

**Yes**

**no**

**Oral glucose**  
**E.g.: Sandwich**  
**or juice, etc...**

**IV access**  
**Dextrose 50% 50ml**  
**No IV access**  
**Glucagon 1mg**  
**IM,SC**

**Monitoring**

Check serum glucose q 30min  $\times$ 4h, repeating management algorithm as needed.  
Consider Dextrose continuous infusion after 2 cycles.

### **Disposition**

Consider discharge after 4h uneventful observation if,

[figure not shown]
- Hypoglycemia fully and rapidly reversed without continuous infusion of dextrose
- Tolerated a full meal in ED
- Clear and innocuous cause identified with recurrence unlikely
- Adequate patient understanding, home support/monitoring, and ability to detect/prevent recurrence with close primary care follow-up

## Ministry of Health hyperkalemia management:

8/5/2022

Document Management System

Home | Login

e-portal/HDoc\_Manage\_System/Document\_Display.aspx?Dispidd=182

2/4

If Potassium is 6.0 – 6.5 mmol/l with no ECG changes

- Exclude pseudohyperkalemia
- Stop all potassium-containing/sparing drugs
- Low potassium diet
- Ensure adequate hydration and monitor urine output
- Treat hypotension
- Monitor renal function

Consider step 2 onwards in addition to below

**Step 3 Reduce Total Body Potassium**

**3a) REDUCE POTASSIUM INTAKE**

- Stop all potassium containing/sparing drugs
- Consider low potassium diet

**3b) Promote Urinary Potassium loss**

By use of appropriate fluids or diuretics

**3c) Remove Excess Potassium**

- Calcium Resonium 15mg PO TID

(This may not be necessary if the obvious cause for hyperkalemia is identified and correct)

- If oral route is not available, calcium resonium enemas can be given as 30g to be retained for 9 hours

Recheck Potassium after 4-6 hours then daily

- Consider stopping Calcium Resonium when  $K^+ < 6.0$  mmol/L.
- Stop treatment when  $K^+ < 5.5$  mmol/L.
- Continue other supportive measures.

**3d) Dialysis**

If patient does not respond to above measures, contact nephrology on call urgently to discuss further management.

## Serious Adverse Event (SAE) Case Log

Principal Investigator: \_\_\_\_\_

IRB Number: \_\_\_\_\_ Protocol Number: \_\_\_\_\_ Subject ID# \_\_\_\_\_

--	--	--	--	--	--

Short Protocol Title: \_\_\_\_\_

SAE Number	SAE Description	Adverse Event* (Select from Safety Profiler)	SAE Classification	Event Start Date	Event End Date	Date Site Became Aware of Event (Reported Date)	Grade	Unexpected (Y or N)	Attribution	Outcome

\*look up corresponding AE at: <https://safetyprofiler-ctep.nci.nih.gov/>

SAE Classification	Grade	Attribution	Outcome
1 - Fatal (resulted in death)	1 - Mild	0 - Definite	0 - Fatal
2 - A life-threatening occurrence	2 - Moderate	1 - Probable	1 - Not recovered/not resolved
3 - Requires inpatient hospitalization or prolongation of existing hospitalization	3 - Severe	2 - Possible	2 - Recovered w/sequelae
4 - Results in persistent or significant disability/incapacity	4 - Life Threatening	3 - Unlikely	3 - Recovered w/o sequelae
5 - Results in congenital anomaly/birth defect	5 - Death (Fatal)	4 - Unrelated	4 - Recovering/Resolving
6 - A significant medical incident that, based upon appropriate medical judgment, may jeopardize the subject and require medical or surgical intervention to prevent one of the outcomes listed above.			

## Subject Deviation/Unanticipated Problem Case Log

### Subject Deviation/Unanticipated Problem Case Log

Principal Investigator: \_\_\_\_\_

IRB Number: \_\_\_\_\_ Protocol Number: \_\_\_\_\_ Subject ID# \_\_\_\_\_

Short Protocol Title: \_\_\_\_\_

--	--	--	--	--

#	Start Date	End Date	Description	Category (see below)	Does the deviation/UP have the potential to:			Reported to IRB	PI Initials	Date of PI Initials
					Impact Subject Safety*	Affect Data Integrity*	Affect Subject's Willingness to Participate?*			
					 Yes  No  Not Applicable	 Yes  No  Not Applicable	 Yes  No  Not Applicable	__/__/__  Not Applicable		
					 Yes  No  Not Applicable	 Yes  No  Not Applicable	 Yes  No  Not Applicable	__/__/__  Not Applicable		

*\*If one or more is answered yes for any event, it must be reported to the IRB promptly (14 business days from notification of or becoming aware of the event).*

**Category:**

1. Consent Deviation
2. Drug/Device Administration/Accountability
3. Enrollment Deviation
4. Procedural Deviation
5. Loss of Confidentiality
6. Other (describe)

Statistical Analysis Plan (SAP)

Title:

5 versus 10 units of insulin in hyperkalemia management:
Prospective, Double blinded, randomized controlled trial,
multicentre, non-inferiority.

(5/10 trial)

Principal investigator:

[name] [name] , Oman medical speciality board, Emergency medicine resident.
[name] [name], Oman medical speciality board, Emergency medicine resident.

Authors:

[name], Oman medical speciality board, Emergency medicine resident.
[name] [name], Emergency medicine, senior consultant Sultan Qaboos University Hospital.
[name] [name], Emergency medicine, senior consultant Sultan Qaboos University Hospital
[name], Emergency medicine, Consultant Sultan Qaboos University Hospital.
[name], Internal medicine, Nephrology Consultant, Sultan Qaboos University Hospital.
Dr: [name], Emergency medicine, consultant, Royal hospital.

Corresponding Author: [name] [name].

Ethical approval:

- Medical Research Ethics Committee (MREC), College of Medicine and Health Sciences, Sultan Qaboos University, MREC#2779. Date:1st june 2022.
- Sultanate of Oman, Ministry of Health Directorate General of Planning & Studies Centre of Studies and Research: MOH/CSR /23/26349. Date: 14/05/2023.

Version number: 001.

Date: 03/08/2023

Table of Contents

Introduction	3
Study design	3
Sample size calculation	3
Aims and objectives	4
Outcomes.....	4
Primary outcome	4
Secondary outcomes.....	4
Safety outcomes	5
Populations	5
Intention-to-treat (ITT)	5
Per Protocol (PP).....	5
Statistical analysis	5
Primary outcome	5
Secondary outcomes.....	6

Introduction

The objective of this research is to evaluate the effects of 5 units of intravenous insulin against 10 units in treating hyperkalemia at the Emergency Department of Sultan Qaboos University Hospital and Royal Hospital. This Statistical Analysis Plan (SAP) provides an in-depth overview of the study's endpoints and their respective analytical methods.

Study design

5 versus 10 units of insulin in hyperkalemia management: multi-center, prospective, double blinded, non-inferiority, randomized control trial in adult patients with age of 18 years and more at two emergency departments Sultan Qaboos university hospital and Royal hospital. We will include patients with potassium level 5.5 mEq/l and more. We will measure the mean reduction of insulin level among both groups at 2 hours from treatment. Written consent will be obtained from all patients. Eligible subjects will be enrolled. Control group will receive 10 units intravenous insulin with Dextrose 50 % 50 ml over 15 minutes and Salbutamol nebulization. Intervention group will receive 5 units intravenous insulin with Dextrose 50 % 50 ml over 15 minutes and Salbutamol nebulization. Patient will be monitored and basic labs will be recorded. Blood sugar will be monitored at 0, 60 and 120 (2 hours) minutes. Potassium level will be measured at presentation and at 120 minutes (2 hours) from insulin administration.

Sample size calculation

We aim to study all hyperkalemia patients who come to the emergency departments of both hospitals. The sample size determination was influenced by a 2020 article in the Critical Care Explorations Journal titled "Comparison of IV Insulin Dosing Strategies for Hyperkalemia in the Emergency Department" authored by Kayvan Moussavi and colleagues. We expect an effect size of $d=0.2$, with an alpha error probability of 0.0250 (one-sided), a true power of 90, a standard deviation of 0.62, and a 1:1 allocation ratio. The sample size deduced is 320, split evenly between both groups. Anticipating a 5% attrition rate, we've adjusted our total sample to 336 participants, with 168 in each group

Aims and objectives

The aim of this study is to compare the efficacy of two insulin doses (5 units and 10 units) in reducing serum potassium level in patients receiving hyperkalemia treatment.

Outcomes

Primary outcome

- To study the efficacy of two intravenous insulin doses (5 units and 10 units) in reducing serum potassium level in patients receiving hyperkalemia treatment using the main laboratory measurements. (the aim of reduction of 0.6 mmol/l +/- 0.2 mmol/L) (1). Blood sample will be collected and send to the main laboratory for analysis at two hours from medications administration. The efficacy of the 2 doses will be measured at 2 hours from administration of medications by comparing the amount of changes in potassium level at two hours.

Secondary outcomes

1. Study the mean difference of the response to the anti-hyperkalemic measures based on the level of initial potassium (serum potassium before given any medications – At baseline) (the investigators will categorize potassium level into groups mild (5.5–6 mmol/l), moderate (6–6.5 mmol/l) and severe (>6.5 mmol/l) and will see the mean difference in reduction in potassium level in between the 2 doses).
2. Association of mean potassium reduction with initial blood sugar level (blood sugar level before given any medications – At Baseline) on potassium reduction (the investigators will categorize blood sugar into groups: Below 10mmol/L, 10.1-14.9 mmol/L, and 15 – 19.9mmol/L among each group the investigators will see the mean potassium reduction level).
3. Incidence of hypoglycemia (random blood sugar (RBS) \leq 3.89 mmol/l in Diabetic patients and less than 3 mmol/l in non-Diabetic patients) (12). (and risk factor Characteristic of patients of higher risk of developing hypoglycemia (the investigators will investigate which group of patients will have a high risk of hypoglycemia ((e.g: initial Glucose level, initial creatinin/renal function, comorbidities, type of dialysis...)).

Safety outcomes

Adverse events are reported at each visit.

Populations

Intention-to-treat (ITT)

All randomized study subjects. This will be seen as the primary population for the analysis.

Per Protocol (PP)

All randomized study subjects completing the whole study period (complete cases). For a specific analysis, study subjects with missing data on any of the variables in the model will be excluded from the analysis. Analyses of this population is seen as a sensitivity analysis to investigate whether conclusions are sensitive to assumptions regarding the pattern of missing data.

Statistical analysis

Primary outcome

The data analysis for the clinical trial will be conducted using IBM SPSS Statistics version 29.0. Categorized variables will be presented as percentages, and continuous variables will be presented as means with standard deviations or medians with interquartile ranges. The primary outcome, the reduction in serum potassium levels, will be analyzed using a linear mixed effect model that adjusts for baseline potassium levels. A p-value of <0.05 will be considered statistically significant.

The intention-to-treat (ITT) analysis will include all subjects who provide at least one post-baseline valid measurement. The per-protocol (PP) analysis will only include subjects who have completed the study according to the protocol and who have valid measurements for all time points. Non-inferiority will be concluded if both the ITT and PP analyses show that the difference in means between the two treatment groups is not statistically significant and lies above the margin of -20 units.

Secondary outcomes

Normally distributed continuous variables will be compared between the groups using Independent 't' test or else with Mann-Whitney 'U' test and categorized levels will be compared using chi-square test. The incidence of hypoglycemia will be presented using percentage with 95% confidence interval. A p-value of <0.05 will be considered as statistical significance.

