#### **Secondary outcome**

1. Study the mean difference of the response to the anti-hyperkalemic measures based on the level of initial potassium (serum potassium before given any medications – At baseline) (the investigators will categorize potassium level into groups mild (5.5–6 mmol/l), moderate (6–6.5 mmol/l) and severe (>6.5 mmol/l) and will see the mean difference in reduction in potassium level in between the 2 doses).
2. Association of mean potassium reduction with initial blood sugar level (blood sugar level before given any medications – At Baseline) on potassium reduction (the investigators will categorize blood sugar into groups: Below 10mmol/L, 10.1-14.9 mmol/L, and 15 – 19.9mmol/L among each group the investigators will see the mean potassium reduction level).
3. Incidence of hypoglycemia (random blood sugar (RBS)  $\leq$  3.89 mmol/l in Diabetic patients and less than 3 mmol/l in non-Diabetic patients) (12). (and risk factor Characteristic of patients of higher risk of developing hypoglycemia (the investigators will investigate which group of patients will have a high risk of hypoglycemia ((e.g: initial Glucose level, initial creatinin/renal function, comorbidities, type of dialysis...)).

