### **16.Limitations and difficulties of the study:**

The large sample size will need to be followed and all data must be kept and organised all time.

Multicentre will have some difficulties as 2 different HIS used in these hospitals.

Funding will be needed for to cover all the logistics and facilitate the flow of the research..

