## 27.Appendix:

### Data collection sheet

Patient hospital ID								
Study Code:								
Demographics								
Hospital								
Location (ED/Inpation)								
Gender								
Age								
DM type								
HTN								
IHD								
ESRD								
Last Dialysis session (if any)								
Other comorbidities								
Home Medications								
Suspected cause of Hyperkalemia								
CBC	Hb:	WBC:	Plat:					
UE	AG:	HCO3:	Creat:	GFR:	Na:	K:		
Mg serum								
Follow up /time line (minutes)	0	60	120					
Potassium								
Blood sugar								
Total amount of Intravenous fluid received during the study period / type of IV fluid								
Other medications administered								
Urine output (if any)								
Needed another antihyperkalemic messures?								
Needed Urgent/Emergent Dialysis?								

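### The primary model is under-specified: it is called mixed with no random effect defined, and it does not say how hospital is handled or use baseline glucose and ESRD, which are already collected

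*SAP*

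**What the plan says.** The SAP (Statistical analysis, Primary outcome) states that the reduction in serum potassium "will be analyzed using a linear mixed effect model that adjusts for baseline potassium levels". That is the whole specification. It gives no random effect, no term for hospital and no other covariate.

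Other parts of the documents bear on this:

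- **One outcome value per patient.** Potassium is taken at baseline and at 120 minutes only (protocol section 7; SAP, Study design).
- **Two hospitals, perhaps more.** Protocol section 5 names two and allows others to be added if recruitment is short. Section 9 mentions randomisation blocks. Neither section 6 nor section 9 states stratification by hospital or by any other factor.
- **Data already collected.** The data collection sheet in section 27 has fields for hospital, ESRD, last dialysis session, creatinine, GFR and blood sugar at time 0.
- **Baseline glucose.** Protocol section 3 lists as a secondary outcome "Association of mean potassium reduction with initial blood sugar level", and the Summary poses the same question.
- **Missing data.** Under the SAP's Populations heading, the per-protocol analysis drops anyone missing a variable in the model. The decision rule requires both the intention-to-treat and the per-protocol analyses to succeed.

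**The concern.** A mixed model needs a grouping factor. With one post-baseline value per patient there are no repeated outcomes to group, so hospital is the only evident candidate, and the SAP does not name it. One analyst could fit a random hospital intercept, another an ordinary regression on baseline potassium, and both could claim to have followed the plan. In a non-inferiority trial decided by where an estimated difference lies against a margin, that choice should not be open once the data are seen.

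The second issue is precision. Prespecified adjustment for baseline variables that predict the outcome narrows the interval and takes account of chance differences between arms in, for example, the share of ESRD patients or of patients from one hospital. No new data are needed.

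**Working it through.** **Inputs.** From the SAP's sample size section: one-sided alpha 0.025, "a true power of 90" (read as 90%), "a standard deviation of 0.62", an effect size of 0.2, and 160 per arm before dropout. Three readings are mine: 0.2 is a margin in mmol/L, the true difference is zero, and 0.62 is the residual SD of the planned model after adjustment for baseline potassium. The SAP states none of these. No document gives the variance explained by hospital, glucose or ESRD, so the extra R² is an assumed range starting at zero.

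**The plan's own figure.** n per arm = 2 × (1.960 + 1.282)² × 0.62² / 0.2² = 202, or 404 in total, against the stated 320. The stated number is not reproduced. At 160 per arm:

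- SE = 0.62 × √(2/160) = 0.0693
- power = Φ(0.2/0.0693 − 1.960) = 82.3%

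That shortfall is a separate fault. It serves here only as the base case.

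**Effect of added covariates.** SE = 0.62 × √(1 − R²) × √(2/160); half-width = 1.96 × SE; power = Φ(0.2/SE − 1.960).

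| Assumed extra R² | SE | 95% half-width | Power |
|---|---|---|---|
| 0 | 0.0693 | 0.136 | 82.3% |
| 2% | 0.0686 | 0.134 | 83.0% |
| 5% | 0.0676 | 0.132 | 84.1% |
| 10% | 0.0658 | 0.129 | 86.0% |
| 15% | 0.0639 | 0.125 | 87.9% |

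The SE falls by 1.0%, 2.5%, 5.1% and 7.8% in the last four rows.

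**Cost in degrees of freedom.** A model with treatment and baseline potassium on 320 patients leaves 317 residual degrees of freedom. Hospital, glucose and ESRD use three more, which inflates the SE by roughly √(317/314) = 1.005. The table leaves this out. The added terms break even at an extra R² of about 3/317, or roughly 1%.

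**What hospital alone could explain.** For two equal-sized centres whose mean reductions differ by Δ, R² = (Δ²/4)/0.62². A difference of 0.2 mmol/L gives 0.01/0.3844 = 2.6%; 0.4 mmol/L gives 0.04/0.3844 = 10.4%. The documents give no value for Δ.

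**Could adjustment restore 90% power?** At 160 per arm, 90% power needs a residual SD of 0.2 × √80 / (1.960 + 1.282) = 0.552. That means an extra R² of 1 − (0.552/0.62)² ≈ 21%, beyond the range shown.

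**The case against.** The strongest reply is that nothing here is an error. In a randomised trial with a linear model, omitting prognostic covariates does not bias the treatment comparison, and the interval already allows for chance imbalance. No stratification is stated, so no covariate is required to match the design. The SAP already adjusts for the outcome's own baseline. The gain may be small: at 2% extra R², power moves by less than one point. All of that stands, and it limits the point to precision and model definition. The per-protocol set is selected after randomisation, so adjustment might do more there, but the documents do not let that be sized and the point does not rest on it.

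Two stronger readings are tempting, and the documents support neither.

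- **That the plan ignores its two-centre design.** A reader might infer this from the missing hospital term. But the model is called mixed, and hospital may be the intended random effect. What can be shown is that the effect is undefined.
- **That the protocol names hospital, renal status and glucose as influences on potassium response.** Only glucose is tied to it, and as a question to be examined. Renal function and type of dialysis are listed as possible risk factors for hypoglycemia. On hospital, section 16 says only "Multicentre will have some difficulties as 2 different HIS used in these hospitals", which concerns information systems.

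An argument from laboratory differences is also weak. The documents speak of the main laboratory, so separate laboratories are an inference. If both of a patient's samples go to the same one, a constant offset cancels in the reduction.

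A practical objection also stands: under the SAP's per-protocol definition, each added covariate is another reason to drop a patient, so a missing-covariate rule must come with the change.

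**Conclusion.** The point holds as a gap in specification with a modest gain in precision on offer. The SAP calls its primary model mixed without defining a random effect, does not say how hospital is handled, and leaves unused baseline data that the trial already collects.

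The gain in power runs from nothing at zero extra R² to about 5.6 points at 15% (82.3% to 87.9%), less a very small degrees-of-freedom cost. This rests on an assumed R², on 0.62 as the residual SD, on 0.2 mmol/L as the margin, on no true difference and on 160 per arm. If 0.62 is the SD before adjustment for baseline potassium, every power in the table would be higher to the extent that baseline potassium predicts the outcome.

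The 82.3% starting point should not be taken as a consequence of the covariate choice, nor adjustment as its cure. It reflects a sample size that does not follow from its own inputs. That fault, and a decision margin of -20 units that does not match the 0.2 used for sizing, are separate and more serious.

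**What to change.** Amend the SAP's primary analysis before unblinding, and before the interim analysis in protocol section 20 if arms are compared there:

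1. **Model.** A linear model for potassium reduction with treatment, continuous baseline potassium and a fixed hospital effect. Drop the word mixed, because two centres estimate a random-effect variance poorly.
2. **Covariates.** Add continuous baseline glucose and ESRD (yes/no). Glucose is the variable the protocol itself links to potassium response, and its value is needed for the exclusion criteria. ESRD is a single field on the sheet.
3. **Missing covariates.** Keep these patients by a simple baseline imputation rule that does not use treatment arm, such as the overall mean for glucose, and amend the per-protocol exclusion sentence to match.
4. **Added centres.** If further hospitals join, state in advance how a small one is pooled.
5. **Sensitivity analysis.** Report the model with baseline potassium alone.

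The cost is a sentence or two in the SAP and the handling of what should be rare missing covariates. No new data or patients are needed.

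### The SAP gives PP two definitions and two roles, and neither ITT nor PP keeps a patient without a 120-minute potassium, so PP cannot be the missing-data check the SAP says it is

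*SAP*

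**What the plan says.** The SAP describes the analysis sets in two places.

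- **Populations.** ITT is "All randomized study subjects. This will be seen as the primary population for the analysis". PP is "All randomized study subjects completing the whole study period (complete cases"), with the addition that, for a given analysis, "study subjects with missing data on any of the variables in the model will be excluded from the analysis". The purpose of PP is then stated: "Analyses of this population is seen as a sensitivity analysis to investigate whether conclusions are sensitive to assumptions regarding the pattern of missing data".
- **Primary outcome text, under Statistical analysis.** Here ITT is worded differently: "The intention-to-treat (ITT) analysis will include all subjects who provide at least one post-baseline valid measurement". The PP "analysis will only include subjects who have completed the study according to the protocol and who have valid measurements for all time points". PP also enters the decision: "Non-inferiority will be concluded if both the ITT and PP analyses show that the difference in means between the two treatment groups" meets the stated conditions.

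On timing, the SAP's Study design section says "Potassium level will be measured at presentation and at 120 minutes (2 hours) from insulin administration". Protocol section 7 gives the same two times. The primary model is a linear mixed model of the reduction, adjusted for baseline potassium. Neither document gives an imputation method or any other analysis for missing potassium.

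Two protocol provisions bear on who is lost. Section 5 allows the treating physician to withdraw a patient, and section 21 makes end-of-study assessments after discontinuation conditional on suitability and feasibility. The footnote to the inclusion criteria and the study flow chart also exclude patients enrolled on a blood gas whose laboratory potassium is later found to be below 5.5 mEq/L. The flow chart adds haemolysed samples.

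**The concern.** The two PP definitions select different patients, and the two roles are different jobs. One is a check on missing-data assumptions; the other is half of the confirmatory rule. An analyst could follow either text, and the choice changes the power of the rule.

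The more important point is structural. A complete-case set can test sensitivity to missing data only if the analysis it is compared with handles the missing patients in some other way. Here it does not. If patients who respond poorly are more likely to leave before 120 minutes, both analyses lose them, both carry the same bias, and their agreement gives no warning. If 5 units is truly worse, that bias favours a non-inferiority finding.

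Neither ITT wording says what happens to a patient already randomised on a blood gas and then excluded on the laboratory result. No size is claimed for that.

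**Working it through.** **Step 1. Who contributes to the primary model.**

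| Set | Text | Patient without 120-min potassium |
|---|---|---|
| ITT, Populations | all randomised | in the set, but has no outcome to model |
| ITT, Primary outcome | some valid post-baseline value | out; or, if a glucose value counts, in but with no outcome |
| PP, Populations | completers with complete model variables | out |
| PP, Primary outcome | compliant completers with all time points | out |

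There is one post-baseline potassium and therefore one reduction per patient, with baseline as a covariate. The mixed model has no second post-baseline potassium from which to recover the missing one. The analysed ITT is the set with a 120-minute potassium. The Populations PP is that same set, apart from patients who withdrew but still gave the sample.

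**Step 2. The plan's own loss figure.** 320 × 1.05 = 336, as stated. If attrition means a missing 120-minute potassium, 0.05 × 336 = 16.8. So 16 or 17 patients lack the outcome, and at most about 320 contribute to either analysis. (The 320 itself does not follow from the stated inputs: 2 × (1.960 + 1.282)² × 0.62² / 0.2² gives 202 per arm. That is a separate matter and nothing here depends on it.)

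**Step 3. Size by formula.** With loss in one arm only, bias = share missing × gap in mean reduction between unseen and seen patients. At 5% missing and a gap of 0.6 mmol/L, the bias is 0.05 × 0.6 = 0.03 mmol/L. A shift of 0.2 would need a gap of 0.2 / 0.05 = 4.0 mmol/L at 5% missing, 2.0 at 10% or 1.33 at 15%.

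**Step 4. Loss related to response in both arms (simulation, 40,000 trials).** From the SAP: 168 per arm, SD 0.62, 5% loss, mean reduction 0.6 in the 10-unit arm. Assumed: margin 0.2 mmol/L, true mean 0.4 in the 5-unit arm, loss correlated ρ with the reduction, further PP exclusions at random, unadjusted comparison, and success if the lower 95% limit exceeds −0.2 in both sets.

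| | ρ = 0 | ρ = 0.5 | ρ = 0.7 |
|---|---|---|---|
| Mean difference (truth −0.200) | −0.200 | −0.191 | −0.182 |
| False non-inferiority, PP = analysed ITT | 2.6% | 3.3% | 4.6% |
| PP loses a further 5% | 2.1% | 2.7% | 3.7% |
| PP loses a further 10% | 1.8% | 2.4% | 3.4% |

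The bias is 0.009 and 0.018 mmol/L. In the first row of rates the ratios to ρ = 0 are 0.0331/0.0258 = 1.3 and 0.0457/0.0258 = 1.8, and the other rows give about the same. A stricter PP lowers the level but leaves the ratio. At 10% loss the first row becomes 2.6, 4.0 and 6.3%. With equal true effects and this same mechanism in both arms, the bias is zero.

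**Step 5. Loss of poor responders in the 5-unit arm only (500 trials per setting, baseline-adjusted, equal true effects).** The bias towards 5 units was +0.025, +0.056 and +0.082 mmol/L at 5, 10 and 15% missing in that arm. ITT minus complete-case PP was exactly 0 in every run. A PP set losing a further 5% at random carried the same bias (0.024, 0.056, 0.082).

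**Step 6. What the PP definition does to power (equal effects, ρ = 0).** Unadjusted, the both-sets rule has 82% power if PP equals the analysed ITT, and 78% or 76% if PP loses a further 5% or 10%. The SAP's model is baseline-adjusted. With an assumed baseline-response correlation of 0.3, the figures are about 85%, 82% and 79 to 80%.

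**The case against.** - **The two ITT wordings can be reconciled.** They can be read as the population and its analysable subset. That is fair. The SAP does not say so, but this is the weakest part of the point and the conclusion does not rest on it.
- **PP is not always the same as ITT.** A reader might infer that the second set is empty of information. The documents do not support that. The Populations PP requires completion, and protocol section 21 allows a discontinued patient still to be assessed, so such a patient can be in ITT and not in PP. The Primary outcome PP can also differ through adherence. PP can therefore inform on adherence and withdrawal. What it cannot address is missing potassium.
- **All time points.** A reader might infer that a patient lacking only the 60-minute glucose leaves PP. That reading is strained: the sentence sits under the primary outcome, and the Populations text ties exclusion to variables in the model, where glucose does not appear.
- **The bias is small and its driver is assumed.** This stands. The correlation has no basis in the documents, and at ρ = 0.5 with a further 10% PP loss the false non-inferiority rate is 2.4%, below the nominal 2.5%. Baseline adjustment changes the figures only slightly: at ρ = 0.7, 4.2, 3.7 and 3.1% for further PP losses of 0, 5 and 10%.
- **Sampling after discontinuation is already foreseen.** Partly so. Section 21 provides for it, but conditionally.

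**Conclusion.** The point holds. PP has two definitions and two roles, and the SAP credits it with testing sensitivity to missing data, which it cannot do for the primary outcome. This follows from the text and needs no assumption beyond one post-baseline potassium and no imputation.

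The numerical effect is modest at 5% loss: about 0.01 to 0.02 mmol/L of bias, and false non-inferiority about 1.3 to 1.8 times its value without response-related loss. Those figures assume a 0.2 mmol/L margin and deficit, the same loss mechanism in both arms, and a proper confidence-limit rule in place of the SAP's wording (including its margin of −20 units), which is a separate and larger problem. They are not a worst case: loss of poor responders confined to the 5-unit arm biases towards 5 units even at equal effects.

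A reader might infer that the trial's conclusion is likely to be wrong on this account. The documents do not support that. The case for change is that the sets in the decision rule are not uniquely defined and that the promised missing-data check is absent.

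**What to change.** Amend before unblinding.

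1. **ITT.** Use one definition in both SAP sections: all randomised patients, analysed as randomised. Fit the primary model with multiple imputation by arm, with baseline potassium in the imputation model, for a missing 120-minute potassium. If patients found ineligible on the pre-treatment laboratory sample are removed, call the set modified ITT, decide removal blind to arm, and report numbers by arm.
2. **PP.** Define it once, by listed adherence criteria, with potassium at 0 and 120 minutes as the required measurements. Keep it in the decision rule, and delete the Populations sentence that makes it the missing-data sensitivity analysis.
3. **Missing-data check.** In its place add a tipping-point analysis that lowers imputed 5-unit reductions by a delta running from 0 to −0.6 mmol/L. The range passes through the SAP's own 0.2 tolerance and ends at its whole expected reduction of 0.6, so roughly no response.
4. **Sampling.** Strengthen protocol section 21 so that the scheduled 120-minute sample is taken after withdrawal from treatment unless consent is withdrawn.

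Limits: imputation from arm and baseline alone assumes that loss does not depend on the unseen response, so it will give nearly the complete-case answer. Items 1 and 3 do not remove the inflation in Step 4; item 3 shows how strong the loss mechanism must be to overturn the result. Item 4 is what reduces the loss itself.

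Cost: SAP wording, a short protocol clarification and one extra analysis. An adherence-based PP in the rule lowers baseline-adjusted power at equal effects from about 85% to about 82% if PP loses a further 5%, or 79 to 80% if it loses a further 10% (assumed baseline correlation 0.3). The sensitivity analysis gets stricter as delta grows. With random 5% loss and equal effects, it succeeds in about 85% of trials at delta 0, 81% at −0.2, 77% at −0.4 and 71% at −0.6.
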